### 9.6.2 Data Monitoring

The de-identified data entered by physicians into LiveTracker™ will be remotely supervised and the following metrics will be collected:

- Percentage of participation and completion
- Physician location, type of practice setting

There will be automated quality control mechanisms built into LiveTracker™ at the time of data entry (e.g., verification of data completeness, standardised response formats, validations and edit checks) in accordance with the data monitoring plan.

### 9.6.3 Record Keeping

The MAH must retain all study records and source documents for the maximum period required by applicable regulations and guidelines, or institution procedures, or for the period specified by the MAH, whichever is longer.

## 9.7 Data Analysis

### 9.7.1 Statistical Analysis Plan

The planned statistical analyses are summarised in sections 9.7.2 to 9.7.6. The statistical analyses will be described in detail in a stand-alone *Statistical Analysis Plan* (SAP) (**Error! Reference source not found.**).

---

### 9.7.2 Analysis Populations

- Primary analyses: The primary analysis population will include the total number of HCPs who returned a valid questionnaire.
- Additional analyses: In order to identify any selection bias, basic variables recorded in the LiveTracker™ database will be compared between the responders and the population of non-responder HCPs from the LiveTracker™ panel.

### 9.7.3 Descriptive Statistics

All assessment data will be summarised using descriptive techniques. Unless otherwise specified, continuous variables will be described by their mean, standard deviation, and median, first quantile (Q1), third quantile (Q3), minimum and maximum. Categorical variables will be described as total number and relative percentage per category.

As a first step, the participant characteristics (practice settings and inclusion criteria) will be described.

### 9.7.4 Primary Analyses

A description of the following outcomes of interest related to process indicators will be performed:

- Measures of the extent of implementation of the original plan, and/or variations in its delivery, at each participating country level.
- Knowledge and Behaviour

For each question, the proportion of HCPs who have provided correct and appropriate answers will be calculated.

Questions common to all HCP types will be analysed for all HCP and by type of HCP (prescribers vs. non-prescribers). Questions specific to prescribers or non-prescribers will be analysed for each type of HCPs.

In addition, the number of correct answers by HCP will be calculated, from which the average number and percentage of correct answers will be computed. The proportion of HCPs who provided correct answers to 70%, 80%, 90% and 100% of the questions will be derived, for all questions, knowledge questions, and behaviour questions.

The threshold of the satisfactory rate is defined as 80% of the HCPs providing correct responses for the following questions:

- 1 The first knowledge question (key question) for both prescribers and non-prescribers;  

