**AND**

- 3 At least two out of three behaviour questions for non-prescribers.

The first knowledge question regarding the safety message “*isatuximab is associated with risk of interference with blood compatibility tests*” is defined as the key question. This knowledge question has more weight than all the other questions to assess the effectiveness of aRMM, because it provides an overarching safety message to inform both prescribing and non-prescribing HCPs about the major risk. Thus, at least 80% of the HCPs are expected to provide correct responses to this key question.

In addition, this threshold of 80% also applies to the behaviour questions—without identification of specific key questions—as part of the satisfactory criteria to assess the effectiveness of aRMM. The rationale for not identifying key questions from these behaviour questions is that prescribers and non-prescribers have different risk mitigation approaches to manage the interference and to avoid possible resulting adverse clinical consequences. Also, prioritization of questions could not be done within the behaviour questions. The pre-defined threshold for correct responses on a proportion of behaviour questions (i.e., 5/7 or 2/3) has been set to be similar between prescribers and non-prescribers.

The satisfactory threshold has been set at 80% to be in line with similar previous research.(10)

This combined approach of a satisfactory threshold of 80% on the key knowledge question and a certain proportion of behaviour questions intends to systematically assess the overall effectiveness of aRMM.

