### **9.7.6 Subgroup Analyses**

In addition to the analyses by HCP type (prescribers and non-prescribers) as described above, analyses will also be performed at country level.

Other sub-groups analysis will include (if sample size allows):

- Characteristics of responders who provided correct answers to 70%, 80%, 90% and 100% of the questions vs responders who did not reach the threshold
- Comparison of responders and non-responder's characteristics
- Comparison of responders and overall target population characteristics
- Analyses among HCPs who actually received the EMs vs. those who did not.

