**Knowledge questions: Q2-Q3**

- 2 **Select true or false for the following statement on isatuximab:**  
*“Isatuximab is associated with risk of interference with blood compatibility tests”\**
  - True
  - False

[Correct answer: True]

PI- List drop down

\*Key safety question

[DP:1]

- 3 **Approximately how long may the isatuximab interference with indirect antiglobulin tests persist after the last infusion of isatuximab?**
  - A. One month
  - B. Three months
  - C. Six months
  - D. One year

[Correct answer: C]

---

PI- List drop down

[DP:1]

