**Behavior questions: Q4-Q10**

**4 Which of the following is correct regarding blood typing and screening?**

- A. Patients should not be blood typed and screened prior to start treatment with isatuximab
- B. Only select patients should be blood typed and screened prior to start treatment with isatuximab
- C. All patients should be blood typed and screened prior to start treatment with isatuximab

[Correct answer: C]

PI- List drop down

[DP:1]

-----Page Break-----

**5 Select true or false for the following statement: “*You should consider phenotyping prior to starting isatuximab treatment, as per local practice*”**

- True
- False

[Correct answer: True]

PI- List drop down

[DP:1]

**6 Select true or false for the following statement: “*If treatment with isatuximab has already started, there is no need to inform the blood bank that the patient is receiving isatuximab*”**

- True
- False

[Correct answer: False]

PI- List drop down

[DP:1]

**7 Select true or false for the following statement regarding the recommended measures of isatuximab treatment: “*In the event of a planned transfusion, notify blood transfusion centre about the risk of interference with indirect antiglobulin tests.*”**

- True
- False

[Correct answer: True]

PI- List drop down

[DP:1]

-----Page Break-----

**8 Select true or false for the following statement regarding the recommended measures of isatuximab treatment: “For timely transfusions, verify standing orders for transfusions to determine if your patient received isatuximab within the last year”**

- True
- False

[Correct answer: True]

PI- List drop down

[DP:1]

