### Knowledge questions: Q2-Q4

**2 Select true or false for the following statement on isatuximab:**

***“Isatuximab is associated with risk of interference with blood compatibility tests”\****

- True
- False

[Correct answer: True]

PI- List drop down

\*Key safety question

[DP:1]

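### The 70/80/90/100% cuts are too fine for item sets of 2 to 9 questions, and on behaviour the lowest cut admits the prescriber success rule (5/7) but excludes the non-prescriber rule (2/3)

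*Protocol*

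**What the plan says.** Section 9.7.4 (Primary Analyses), after the per-question proportions and the number of correct answers per HCP, adds: "The proportion of HCPs who provided correct answers to 70%, 80%, 90% and 100% of the questions will be derived". This is to be done on three item sets: the whole questionnaire, the knowledge items alone and the behaviour items alone. The Abstract repeats the four levels under its main analysis.

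Section 9.7.6 reuses them to divide responders: "Characteristics of responders who provided correct answers to 70%, 80%, 90% and 100% of the questions vs responders who did not reach the threshold". It names four levels but a single threshold, does not say which item set is meant, and applies only if the sample size allows.

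The success criteria in section 9.7.4 are separate. They require 80% of HCPs to answer the key knowledge question correctly, 80% of prescribers to answer at least five of seven behaviour questions correctly, and 80% of non-prescribers to meet the third rule: "At least two out of three behaviour questions for non-prescribers". The same section says that the two behaviour fractions were chosen to be alike for the two HCP types.

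Appendix C fixes the item counts. For prescribers it lists "Knowledge questions: Q2-Q3" and "Behavior questions: Q4-Q10", that is 2 and 7 items. For non-prescribers it lists "Knowledge questions: Q2-Q4", then behaviour questions 5 to 7, that is 3 and 3 items. Section 9.6.1 counts a survey as valid only when every question is answered, so the denominators do not vary between respondents.

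**The concern.** Percentage cuts ten points apart need sets of about ten items or more to be told apart. The sets here have 2, 3, 6, 7 and 9 items, so several planned rows must be copies of one another.

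The more serious effect is on the behaviour set. The lowest cut, 70%, lies between the two success fractions. The same report would then count a non-prescriber with two of three behaviour items correct as meeting the success rule and, in the threshold table, as below the lowest level. A prescriber who just meets the corresponding rule is treated consistently in both places. A reader comparing the two HCP types in the threshold table would see a difference produced by the cut and not by behaviour. If the 9.7.6 split is made on behaviour items, respondents who met the success rule would be profiled among those who did not reach the threshold.

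**Working it through.** **Inputs.** Cuts of 70, 80, 90 and 100% (section 9.7.4). Item counts from Appendix C: prescribers 2 knowledge + 7 behaviour = 9; non-prescribers 3 knowledge + 3 behaviour = 6. Success fractions from section 9.7.4: 5/7 and 2/3. Direction of the cut: section 9.7.4 does not word it, but section 9.7.6 contrasts reaching the level with not reaching it ("vs responders who did not reach the threshold"), so I read it as at least.

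**The plan's own fractions.** The protocol prints no computed result for these cuts. The success rules are 5/7 = 71.4% and 2/3 = 66.7%.

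**Step 1: cuts as whole items.** For k items and cut c, the number needed is the smallest i with i/k ≥ c.

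| Set | k | 70% | 80% | 90% | 100% | Distinct cuts |
|---|---|---|---|---|---|---|
| Prescriber knowledge | 2 | 2 | 2 | 2 | 2 | 1 |
| Prescriber behaviour | 7 | 5 | 6 | 7 | 7 | 3 |
| Prescriber all | 9 | 7 | 8 | 9 | 9 | 3 |
| Non-prescriber knowledge | 3 | 3 | 3 | 3 | 3 | 1 |
| Non-prescriber behaviour | 3 | 3 | 3 | 3 | 3 | 1 |
| Non-prescriber all | 6 | 5 | 5 | 6 | 6 | 2 |

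The 12 planned non-prescriber figures reduce to 1 + 1 + 2 = 4, and the 12 prescriber figures to 1 + 3 + 3 = 7. If the wording were read as exactly 70, 80 or 90%, no set could attain any of these; only 100% is attainable.

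**Step 2: success rule against the lowest behaviour cut.** Prescribers: 71.4% ≥ 70%, so the rule and the 70% cut are the same event, at least 5 of 7. Non-prescribers: 66.7% < 70%, so the 70% cut requires 3 of 3 and is stricter than the rule.

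**Step 3: size on the behaviour set.** The protocol gives no item accuracy. As an illustration, assume independent items, each correct with probability p. The non-prescribers who meet the rule but miss the cut are those with exactly 2 of 3 correct, a share of 3p²(1−p).

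| p | Non-prescribers ≥ 2/3 | Non-prescribers 3/3 (the 70% cut) | Gap, 3p²(1−p) | Prescribers ≥ 5/7 (rule and 70% cut) |
|---|---|---|---|---|
| 0.7 | 78.4% | 34.3% | 44.1 points | 64.7% |
| 0.8 | 89.6% | 51.2% | 38.4 points | 85.2% |
| 0.9 | 97.2% | 72.9% | 24.3 points | 97.4% |

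With the 40 to 100 non-prescribers targeted in Table 3 and p = 0.8, the gap is 0.384 × 40 ≈ 15 to 0.384 × 100 ≈ 38 respondents. At that same accuracy the 70% behaviour row would show 85.2% of prescribers against 51.2% of non-prescribers, a 34-point difference with no difference in item accuracy behind it.

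**Step 4: all-questions set.** A non-prescriber with 2/3 behaviour items scores (2 + 3)/6 = 83.3% with all three knowledge items correct, which reaches the 80% cut. With two knowledge items correct the score is (2 + 2)/6 = 66.7%, below 70%. A prescriber at 5/7 scores (5 + 2)/9 = 77.8% with both knowledge items and (5 + 1)/9 = 66.7% with one. On this set the mismatch is conditional and affects both HCP types.

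**The case against.** Four counter-arguments deserve a hearing.

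- **The decision rule is untouched.** Success rests on the key question, 5/7 and 2/3; the percentage cuts are an additional description. A stricter descriptive level giving a lower proportion than a minimum rule is not in itself a contradiction. This stands, and it limits the point to the displays and the 9.7.6 split.
- **Little information is lost.** Section 9.7.4 also calls for results per question and for the number and average percentage of correct answers. That answers the duplicated rows. It does not answer the unequal treatment of the two HCP types at the 70% behaviour level.
- **The mapping to whole items belongs in the SAP.** The SAP can define the mapping, but the protocol has already fixed the cuts, the sets and the rules. Rounding to the nearest item (0.7 × 3 = 2.1, so 2; 0.8 × 3 = 2.4, so 2) would bring 2/3 into line, but only by labelling a 66.7% score as both 70% and 80%. No mapping yields four separate cuts on three items.
- **The gap depends on an assumed p and on independence.** True, hence the range above. The ordering of 66.7%, 70% and 71.4% needs no assumption.

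Some stronger readings are tempting but unsupported. A reader might infer that the cuts do not exist on the short sets; 100% exists in every set, and the 6-item set keeps two levels. A reader might infer that 9.7.6 will always place a non-prescriber with 2/3 among those below the threshold; that section names no item set, and step 4 shows an exception on the all-questions set. A reader might infer that a behaviour figure pooled over HCP types is planned. The Abstract does mention overall results, but section 9.7.4 analyses type-specific questions within each type, and every behaviour item is type-specific. The text is ambiguous on pooling.

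**Conclusion.** The point holds for the descriptive threshold tables and the responder split, and no further. The four cuts cannot be told apart on the 2- and 3-item sets, reduce to two on 6 items, and to three on 7 and 9 items. On behaviour, the 70% cut separates two success rules that the protocol treats as equivalent, to the disadvantage of non-prescribers only. Both statements follow from Appendix C and section 9.7.4, given the at-least reading.

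The size of the resulting gap, 24 to 44 percentage points for p between 0.9 and 0.7, is illustrative and rests on independent items of equal accuracy. It should not be read as casting doubt on the study's overall conclusion about effectiveness, because none of the three 80% criteria uses these cuts. It merits correction before the tables are programmed.

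**What to change.** In section 9.7.4 and the Abstract, replace the percentage cuts with item counts for each HCP type:

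- Behaviour, prescribers: at least 5/7, at least 6/7, and 7/7.
- Behaviour, non-prescribers: at least 2/3, and 3/3.
- Knowledge: the full score distribution for each HCP type (0 to 2 and 0 to 3 items).
- All questions, if kept: counts out of 9 and out of 6, shown by HCP type.

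State that behaviour cuts are not pooled across HCP types. In section 9.7.6, name the item set used for the split and, for behaviour, use the protocol's own 5/7 and 2/3 rules.

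The cost is revised table shells. The questionnaire, data collection and sample size do not change. The one drawback is less direct comparability with any external report that uses percentage cuts.

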**AND**

- 2 At least five out of seven behaviour questions for prescribers;

**AND**

- 3 At least two out of three behaviour questions for non-prescribers.

The first knowledge question regarding the safety message “*isatuximab is associated with risk of interference with blood compatibility tests*” is defined as the key question. This knowledge question has more weight than all the other questions to assess the effectiveness of aRMM, because it provides an overarching safety message to inform both prescribing and non-prescribing HCPs about the major risk. Thus, at least 80% of the HCPs are expected to provide correct responses to this key question.

In addition, this threshold of 80% also applies to the behaviour questions—without identification of specific key questions—as part of the satisfactory criteria to assess the effectiveness of aRMM. The rationale for not identifying key questions from these behaviour questions is that prescribers and non-prescribers have different risk mitigation approaches to manage the interference and to avoid possible resulting adverse clinical consequences. Also, prioritization of questions could not be done within the behaviour questions. The pre-defined threshold for correct responses on a proportion of behaviour questions (i.e., 5/7 or 2/3) has been set to be similar between prescribers and non-prescribers.

The satisfactory threshold has been set at 80% to be in line with similar previous research.(10)

This combined approach of a satisfactory threshold of 80% on the key knowledge question and a certain proportion of behaviour questions intends to systematically assess the overall effectiveness of aRMM.

### **9.7.5 Exploratory Analyses**

Of note, similar aRMMs were distributed to HCPs in Europe after the market authorisation was granted to the first-in-class compound (daratumumab). A research article published in February 2021 reported that a total of 408 participants completed the questionnaires. The risk and content of educational materials developed for daratumumab are similar and one can assume that the target population of HCPs is also similar to that of isatuximab. Therefore, a discussion about the proportions observed after the implementation of the risk minimisation measures could be considered against those reported from the daratumumab survey (i.e. pre-post designs), provided that they are available (i.e. publicly disclosed) at the time of this study report preparation/submission.

However, due to the lack of access to patient-level data, no statistical comparison will be performed.

### **9.7.6 Subgroup Analyses**

In addition to the analyses by HCP type (prescribers and non-prescribers) as described above, analyses will also be performed at country level.

Other sub-groups analysis will include (if sample size allows):

- Characteristics of responders who provided correct answers to 70%, 80%, 90% and 100% of the questions vs responders who did not reach the threshold
- Comparison of responders and non-responder's characteristics
- Comparison of responders and overall target population characteristics
- Analyses among HCPs who actually received the EMs vs. those who did not.

### 9.7.7 Handling of Missing Data

No imputation method will be used to replace missing data.

### 9.7.8 Statistical Software

The analyses will be performed using the statistical software SAS®, Version 9.4 (SAS Institute Inc. Cary, NC).

## 9.8 Quality Control

The procedures to ensure data quality and integrity, including the accuracy and legibility of the data collected storage of records, and archiving of the statistical programming performed to generate the results will be extensively described in the *Data Management Plan* and the SAP. Both documents will be stand-alone documents (**Error! Reference source not found.**).

## 9.9 Limitations of the Research Methods

All data supplied will be self-reported by the HCP, and it will not be possible to objectively verify information. The number of HCPs included will vary among countries, so the precision of country-level subgroup analyses will vary. The study uses descriptive statistics only. Therefore, it is not possible to determine whether findings are statistically significant or could be due to chance. However, given that the main objectives are to describe implementation of the aRMMs and to assess knowledge and behaviours, descriptive statistics are sufficient.

The survey will be completed by HCP on a voluntary basis. Thus, there is always the possibility that HCP accepting to participate will have different characteristics and different behaviours than non-responders. In order to identify any such selection bias, the characteristics of responders and non-responders will be described. Detailed description on minimizing selection bias during recruitment can be found in Section 9.2.

In addition, in order to reduce information bias and the possible Hawthorne effect, questions will be close-ended to avoid errors in interpreting free-texts during assessment; questions in questionnaire will not be revealed before the HCP opens it; HCPs will not have the possibility to come back and change their answers once submitted and will not be contacted to clarify or revise their survey responses. The results will reflect the knowledge, understanding and

 Non-responder's characteristics available in the LiveTracker™ panel profile.

 Overall target population characteristics available in the LiveTracker™ panel profile.

behaviour in countries where isatuximab was launched in 2020 or planned to be launched by early 2021, therefore not fully representative of all European countries where isatuximab will eventually be used. In addition, the volume of isatuximab use in the selected countries could also vary and may fluctuate, therefore, the proportion of HCPs in selected countries is based on the potential pool of HCPs rather than the volume of isatuximab use in each country. The educational material distribution strategy the definition and size of the target audience is expected to vary across countries. Consequently, the proportion of HCPs having received the educational material among the invited and participating HCPs might also vary across countries. The implementation results will need to be interpreted in the light of each country-specific distribution strategy.

## **10 Protection of Human Subjects**

### **10.1 Subject Information and Consent**

HCPs will be informed of the modalities and procedures of the survey and will be asked to provide their consent to participate in the survey.

### **10.2 Data Protection**

The data must be collected and processed with adequate precautions to ensure confidentiality and compliance with applicable data privacy protection laws and regulations. No subject-identifying information will be collected. The data collected will be pseudonymised (anonymous to study staff and MAH).

### **10.3 Ethics Committees**

The MAH will ensure that any required approvals from Ethics Committees, Independent Review Committees, Regulatory Authorities, and/or other local governance bodies are obtained before study initiation in each participating country.

